9.10.6. Procedure if the trial is put on hold

If the trial is put on hold by the investigator, iSRC or IDMC because a pre-defined holding rule is met or because of a safety concern, then all enrolment in the study and all vaccination will cease immediately, but all other procedures relating to safety, immunology and disease monitoring will continue. The IDMC will review all available safety information and may ask for additional information to be provided by the investigators or the sponsor. The IDMC will make a recommendation to the sponsor whether the study should be stopped permanently, modified or continued unchanged.

The sponsor will review all data and IDMC recommendation and will decide whether to stop permanently, modify or continue the conduct of the study. The decision of the Vaccine safety monitoring board (VSMB) regarding the further conduct of the study will be documented and provided in writing to the investigators.

10. SUBJECT COMPLETION AND WITHDRAWAL

10.1. Subject completion

A subject who returns for the concluding visit foreseen in the protocol is considered to have completed the study.

10.2. Subject withdrawal

Withdrawals will not be replaced.

10.2.1. Subject withdrawal from the study

From an analysis perspective, a 'withdrawal' from the study refers to any subject who did not come back for the concluding visit foreseen in the protocol.

All data collected until the date of withdrawal/last contact of the subject will be used for the analysis.

A subject is considered a 'withdrawal' from the study when no study procedure has occurred, no follow-up has been performed and no further information has been collected for this subject from the date of withdrawal/last contact.

Investigators will make an attempt (e.g. three telephone calls and a certified letter to the last known address) to contact those subjects who do not return for scheduled visits or follow-up.

Information relative to the withdrawal will be documented in the eCRF. The investigator will document whether the decision to withdraw a subject from the study was made by the subject's parent(s)/LAR(s), or by the investigator, as well as which of the following possible reasons was responsible for withdrawal:

- SAE.
- Non-SAE.
- Protocol violation (specify).
- Consent withdrawal, not due to an AE*.
- Moved from the study area.
- Lost to follow-up.
- Other (specify).

*In case a subject is withdrawn from the study because the subject's parent(s)/LAR(s) has withdrawn consent, the investigator will document the reason for withdrawal of consent, if specified by the subject's parent(s)/LAR(s), in the eCRF.

Subjects who are withdrawn from the study because of SAEs/AEs must be clearly distinguished from subjects who are withdrawn for other reasons. Investigators will follow subjects who are withdrawn from the study as result of a SAE/AE until resolution of the event (see Section 9.5.2).

10.2.2. Subject withdrawal from investigational vaccine

A 'withdrawal' from the investigational vaccine refers to any subject who does not receive the complete treatment, i.e. when no further planned dose is administered from the date of withdrawal. A subject withdrawn from the investigational vaccine may not necessarily be withdrawn from the study as further study procedures or follow-up may be performed (safety or immunogenicity) if planned in the study protocol. The investigator should make all efforts to ensure that the subjects remain in the study to ensure a proper safety follow-up and medical care if needed.

Information relative to premature discontinuation of the investigational vaccine will be documented on the Vaccine Administration screen of the eCRF. The investigator will document whether the decision to discontinue further vaccination was made by the subject's parent(s)/LAR(s), or by the investigator, as well as which of the following possible reasons was responsible for withdrawal:

- SAE.
- Non-SAE.
- Other (specify).

10.3. Extension study

At the end of the study (study conclusion visit), the investigator will ask each subject's parent(s)/LAR(s) if they are interested to allow the subject to participate in a booster study/long-term study. If subject's parent(s)/LAR(s) are not interested in participating in the booster study/long-term study the reason for refusal will be documented in the subject's eCRF.

10.4. Screen and baseline failures

Screening failures are defined as subjects who are withdrawn from the study after giving informed consent, but who do not meet the inclusion and exclusion criteria.

The following information will be collected for screening failures:

- Informed consent.
- Inclusion/exclusion criteria.
- Demographic data.
- Medical history.

- Physical examination.
- Growth monitoring.
- Blood samples for RSV serostatus, hematology and biochemistry, CMI response and humoral response.
- SAEs related to study participation, to concomitant use of GSK products or any fatal SAEs.
- Screening conclusion.

11. STATISTICAL METHODS

11.1. Primary endpoint

- Occurrence of AEs from first vaccination (Day 0) up to Day 60.
 - Occurrence of each solicited local and general AE, during a 7-day follow-up period after each vaccination (i.e. the day of vaccination and 6 subsequent days).
 - Occurrence of any unsolicited AE, during a 30-day follow-up period after each vaccination (i.e. the day of vaccination and 29 subsequent days).
 - Occurrence of any SAE from Day 0 up to Day 60.
 - Occurrence of episode of spontaneous or excessive bleeding (AE of specific interest), during a 30-day follow-up period after each vaccination.
 - Occurrence of any hematological (hemoglobin level, white blood cells and platelets) laboratory abnormalities at Screening, Day 1, Day 7, Day 30, Day 31, Day 37, and Day 60.
 - Occurrence of any biochemical (alanine aminotransferase, aspartate aminotransferase and creatinine) laboratory abnormalities at Screening, Day 30, and Day 60.

11.2. Secondary endpoints

- Occurrence of SAEs from study start (Day 0) up to study conclusion (Day 730).
- Occurrence of RSV-LRTI (AE of specific interest) as from Dose 1 administration up to study conclusion (Day 730).
- Occurrence of RSV-RTI, RSV-LRTI, severe RSV-LRTI (according to standardized case definitions) as from Dose 1 administration up to study conclusion (Day 730).
- Magnitude of the CMI response to the investigational RSV vaccine, pre-vaccination (Screening), post-Dose 1 (Day 30) and post-Dose 2 (Day 60 and Day 365).
 - CD3+/CD4+ T-cells expressing at least two markers among CD40L, IL-2, TNF- α , and IFN- γ upon stimulation with F, N and M2-1 peptide pools.

- Humoral response to the investigational RSV vaccine, pre-vaccination (Screening), post-Dose 1 (Day 30) and post-Dose 2 (Day 60 and Day 365):
 - Neutralizing antibody titers against RSV-A.
 - RSV F antibody concentrations.
- Humoral response to the investigational RSV vaccine, pre-vaccination (Screening), post-Dose 1 (Day 30) and post-Dose 2 (Day 60):
 - Palivizumab-competing antibody concentrations.

11.3. Tertiary endpoints

- CMI response profile (Th1, Th2, Th17) to the investigational RSV vaccine, pre-vaccination (Screening), post-Dose 1 (Day 30) and post-Dose 2 (Day 60 and Day 365).
 - CD3+/CD4+ and/or CD3+/CD8+ T-cells expressing at least one or any combination of immune marker(s) among CD40L, 41BB, IL-2, TNF- α , IFN- γ , IL-13 and IL-17 upon stimulation with F, N and M2-1 peptide pools.
- Any further exploratory immunology to detect disease-related or vaccine-related immune responses, such as but not limited to:
 - Anti-vector immunity: neutralization.

[figure not shown]
11.4. Determination of sample size

No hypothesis driven sample size calculation was conducted due to the nature of descriptive summary of the study objectives. The sample size of 32 subjects per dose cohort/Step, randomized 1:1 to vaccine or placebo, was based on conventional study designs for Phase 1/2 trials. Specifically, if no adverse event was observed among 16 RSV vaccinated subjects, the exact, two-sided 95% confidence interval (CI) would rule out an AE rate of 20% or more; if the incidence rate of AEs is more than 10%, there will still be more than an 80% chance of observing at least one subject with this AE. Combining all RSV vaccinees across all dose levels, there will be more than a 99% chance of observing at least one subject with this AE.

Furthermore, with 16 RSV vaccinees, the maximum width of a 95% CI for the proportion of subjects with adverse events among 16 vaccinees is about 50% (see [Figure 5](#)). (Amended 10 December 2017)

[Figure 5](#) illustrates the precision on the percentage of subjects with symptoms following vaccination.

Figure 5 Exact 95% confidence interval on the percentage of subjects with adverse events following vaccination for 16 subjects per group

Taking the a priori safety concern of thrombocytopenia, both Frequentist and Bayesian approaches will be applied here to provide complementary assurance on the possibility to exclude a signal based on the accumulated safety data. The Frequentist approach examines the statistical power to rule out a significant decrease in platelet counts due to vaccination that would suggest a four-fold or greater increase in the risk of a Grade 3 or higher thrombocytopenia with 16 subjects per dose cohort. The Bayesian approach calculates the posterior predictive probability of not observing any subject with a Grade 3 or higher thrombocytopenia among the future 16 subjects by basing it on what we have observed in the first 16 subjects.

If we assume platelet counts in healthy infants between 12 and 23 months follow a normal distribution with a mean of 300,000 platelets/mm³ and a standard deviation of 75,000 platelets/mm³, then we would expect 0.04% of unvaccinated infants to have a count below 50000 platelets/mm³, which is the cut-off for a Grade 3 thrombocytopenia. To rule out a four-fold or greater increase, we would need to show that the mean platelet count does not fall below 190,000 platelets/mm³ with a standard deviation of 47,500. The sample size needed to rule out a 110,000 platelets/mm³ decrease due to vaccination with 84% power when vaccination has no effect on platelet count is 16 infants per dose cohort (8 per group). Sample size is based on a one-sided 0.025 test of non-inferiority using the Mann-Whitney statistic (PASS 12, Non-inferiority Tests for Two Means using Differences).

The Bayesian approach to predict the probability of no Grade 3 or higher thrombocytopenia in the future 16 subjects per dose cohort will be conducted by treating the mean of platelet counts μ as a random variable with a normal prior distribution $N(\mu_0, \sigma_0^2)$, where μ_0 and σ_0 will be determined by using laboratory normal

range. For this analysis the range of 150,000 to 450,000 platelets/mm³ will be the focus. Based on this laboratory range, μ_0 would be 300,000, a mean of the range, and σ_0 would be 75000, an approximate of a standard deviation of data sampled from this normal range. After 16 infants complete the two-dose vaccination schedule, a posterior distribution of μ will be calculated based on the prior of μ and the observed platelet counts from Day 31. The posterior predictive probability of no Grade 3 or higher thrombocytopenia in the future 16 subjects per dose cohort will be calculated, and sensitivity on the prior will be assessed.

After the first 16 infants of a dose cohort have completed the two-dose vaccination schedule, the 95% CI for the difference in mean platelets at Day 31 between vaccinees and placebo recipients will be calculated along with the posterior predictive probability of no Grade 3 or higher thrombocytopenia in the future 16 infants. If the lower boundary of the 95% CI is above 110,000 platelets/mm³ and the predictive probability is sufficiently high (e.g., 80% or more), the IDMC may recommend enrolling infants into the next dose cohort without completing enrolment in the current cohort. However, if a Grade 3 or higher thrombocytopenia occurs in a vaccinated infant at any time point or if there is a significant safety concern with another laboratory parameter such as hemoglobin or neutrophils, the IDMC may recommend continuing enrolment into the lower dose cohort. (Amended 10 December 2017)

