 - Epoch 002: follow-up starting at Visit 10 (Day 365) and ending at Visit 11 (Day 730).

Any safety, immunogenicity and disease surveillance data collected beyond Visit 9 (Day 60) will be collected in Epoch 002.

- Primary completion Date: Visit 9 (Day 60).
Refer to [glossary of terms](#) for the definition of primary completion date.
- End of Study: Last testing results released of samples collected at Visit 11 (Day 730).*

* Up to Visit 11 (Day 730), there will be monthly nasal swab to detect asymptomatic RSV infections during the RSV season and if following active or a passive surveillance contacts, a subject presents symptoms of RTI, a nasal swab will be collected.

Refer to [glossary of terms](#) for the definition of end of study.

- Study groups: throughout the three steps, infants will be randomized in two groups to receive either ChAd155-RSV vaccine or placebo ([Table 1](#)).

Table 1 Study groups and epochs foreseen in the study (Amended 10 December 2017)

Step	Study groups	Number of subjects*	Age (Min/Max)	Epochs	
				Epoch 001	Epoch 002
1	RSV-Ld	~ 16	12 months - 23 months	x	x
	Placebo-Ld	~ 16	12 months - 23 months	x	x
2	RSV-Md	~ 16	12 months - 23 months	x	x
	Placebo-Md	~ 16	12 months - 23 months	x	x
3	RSV-Hd	~ 16	12 months - 23 months	x	x
	Placebo-Hd	~ 16	12 months - 23 months	x	x

RSV-Ld: low dose ChAd155-RSV vaccine (5×10^9 vp); **RSV-Md:** middle dose ChAd155-RSV vaccine (1.5×10^{10} vp); **RSV-Hd:** high dose ChAd155-RSV vaccine (5×10^{10} vp).

***The target will be to enroll up to 96 RSV-seropositive infants aged 12 to 23 months at the time of first vaccination (unless the dose escalation IDMC decision can be made based on the evaluation of accumulating safety data on fewer subjects) to ensure that at least 64 infants receive two doses of study vaccine (ChAd155-RSV or Placebo) (see Section 5.1). Then the number of subjects at each step will be at least 16 (approximately 8 subjects per group) at steps 1 and 2 and 32 (approximately 16 subjects per group at step 3) (Amended 10 December 2017).**

Table 2 Study groups and treatment foreseen in the study

Treatment name	Volume administered	Vaccine/Product name	Study Groups					
			Step 1		Step 2		Step 3	
			RSV-Ld	Placebo-Ld	RSV-Md	Placebo-Md	RSV-Hd	Placebo-Hd
ChAd155 5x10 ⁹ vp	0.5 ml	ChAd155-RSV	X					
ChAd155 1.5x10 ¹⁰ vp	0.15 ml	ChAd155-RSV			X			
ChAd155 5x10 ¹⁰ vp	0.5 ml	ChAd155-RSV					X	
Placebo 0.5	0.5 ml	Formulation buffer S9b		X				X

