### 11.2. Statistical Method References

The exact two-sided 95% CIs for a proportion within a group will be the Clopper-Pearson exact CI [Clopper CJ, Pearson ES. The use of confidence or fiducial limits illustrated in the case of binomial. *Biometrika*. 1934; 26:404-413].

The standardised asymptotic two-sided 95% CI for the group difference in proportions is based on the method described in the following paper: Robert G. Newcombe, interval estimation for the difference between independent proportions: comparison of eleven methods, *Statist Med*. 1998; 17, 873-890]. The standardised asymptotic method used is the method six.

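### Protocol 11.4 slightly overstates its safety precision: no events in 16 vaccinees does not exclude a 20% AE rate (upper limit 20.6%), and the pooled detection chance above 99% needs at least 44 vaccinees

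*Protocol*

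**What the plan says.** Protocol 11.4 states that no hypothesis-driven calculation was done and starts from "The sample size of 32 subjects per dose cohort/Step, randomized 1:1 to vaccine or placebo". That is 16 vaccinees per step and 48 over three steps. It then describes what this size delivers:

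- Zero-event precision: "if no adverse event was observed among 16 RSV vaccinated subjects", then "the exact, two-sided 95% confidence interval (CI) would rule out an AE rate of 20% or more".
- Detection in one group: "if the incidence rate of AEs is more than 10%, there will still be more than an 80% chance of observing at least one subject".
- Pooled detection: "Combining all RSV vaccinees across all dose levels, there will be more than a 99% chance of observing at least one subject with this AE".
- A maximum 95% CI width of about 50% for 16 vaccinees.

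SAP 11.2 fixes the method: "The exact two-sided 95% CIs for a proportion within a group will be the Clopper-Pearson exact CI".

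The amendment that last revised 11.4 (10 December 2017) also lets Steps 1 and 2 close early. The footnote to Table 1 in Protocol Section 3 says: "Then the number of subjects at each step will be at least 16 (approximately 8 subjects per group) at steps 1 and 2", with about 16 per group kept in Step 3. Protocol 1.3 accordingly puts the number of infants exposed to the vaccine at between 32 and 48.

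**The concern.** The first statement names an interval (exact, two-sided, 95%) and a bound (20%), so it can be checked directly, and it fails. The second is true for 48 vaccinees but reads as a property of the study, while the plan allows a third fewer.

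Both sentences tell ethics committees, regulators and the IDMC how much a clean safety record would mean in a first paediatric study. Someone relying on them would credit the design with slightly more than it has. With zero events the excluded rate is a little higher than stated. If both early steps close at their minimum, the chance of missing an AE with a 10% rate across all dose levels is 3.4% rather than under 1%.

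**Working it through.** **Inputs.** From Protocol 11.4: n = 16 with no events, two-sided 95% exact interval, true AE rate 10%, 48 vaccinees at full enrolment. From SAP 11.2: Clopper-Pearson. From Protocol 1.3 and the Table 1 footnote in Section 3: as few as 8 + 8 + 16 = 32 vaccinees.

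**Formulas.** The Clopper-Pearson upper limit for 0/n is 1 − 0.025^(1/n). The chance of at least one event at rate p is 1 − (1 − p)^n.

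**Figures in 11.4 that reproduce.**
- One group of 16 at a 10% rate: 1 − 0.9^16 = 81.5%, as stated (above 80%).
- Pooled, 48 vaccinees: 1 − 0.9^48 = 99.4%, as stated (above 99%).
- Maximum exact CI width at n = 16: 50.7%, as stated (about 50%).

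**The figure that does not.**
- 0/16: 1 − 0.025^(1/16) = 20.59%. The value 20% lies inside the interval.
- The same result seen another way: at a true rate of 20%, the chance of no events in 16 is 0.8^16 = 2.81%. This exceeds the 2.5% allowed in one tail, so 20% is not rejected.
- 0/17: 1 − 0.025^(1/17) = 19.51%. Seventeen is the smallest number that excludes 20%.

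**Other interval choices for 0/16.**

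| Method | Upper limit |
|---|---|
| Clopper-Pearson, two-sided | 20.6% |
| Blaker (exact, two-sided) | 20.1% |
| Sterne (exact, two-sided) | 20.8% |
| Agresti-Coull | 22.7% |
| Wilson | 19.4% |
| Rule of three | 18.75% |
| Exact, one-sided 95% | 17.1% |
| Mid-P | 17.1% |
| Jeffreys | 14.3% |

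All three exact two-sided methods exceed 20%. Those that fall below are one-sided or not exact, and 11.4 names neither kind.

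**Pooled detection at a 10% rate over the permitted range.**

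| Vaccinees | How reached | Chance of at least one event |
|---|---|---|
| 32 | Steps 1 and 2 both close at the minimum | 1 − 0.9^32 = 96.6% |
| 40 | one of them closes at the minimum | 1 − 0.9^40 = 98.5% |
| 43 | | 1 − 0.9^43 = 98.9% |
| 44 | smallest total above 99% | 1 − 0.9^44 = 99.03% |
| 48 | full enrolment | 1 − 0.9^48 = 99.4% |

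With 32 vaccinees, passing 99% needs a true rate of about 13.4%, since 1 − 0.01^(1/32) = 0.134.

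**A single group of 8, for information.** Upper limit for 0/8: 1 − 0.025^(1/8) = 36.9%. Detection chance at a 10% rate: 1 − 0.9^8 = 57.0%.

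**The case against.** The strongest reply is that little turns on this, and most of it stands.

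The pooled figure is not a miscalculation. Section 11.4 opens with 32 subjects per step at 1:1, and on that basis 99.4% is correct. The lower figures arise only if the IDMC recommends early escalation, and the 32 to 48 range is disclosed elsewhere in the protocol. What remains is a missing condition. The same amendment did add one to the holding-rule risk assessment (Protocol 9.10.5), which now refers to a maximum of 16 per group; the pooled sentence in 11.4 has no counterpart.

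The gap between 20% and 20.6% is small and would round to nothing in a looser sentence. But the text claims exclusion at a named bound, using a named interval, and the interval does not deliver it.

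A reader might infer three stronger things that the documents do not support:

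- That a clean group would be reported as excluding 20%. SAP 6.4.1.1 tabulates exact 95% CIs for AE percentages and SAP 11.3.7 prints limits to one decimal. A group with 0/16 would show 20.6.
- That these two sentences are the only support for the sample size. Section 11.4 also cites convention for Phase 1/2 trials, the detection chance in one group, the CI width and a platelet calculation. Protocol 9.10.5 adds holding-rule operating characteristics.
- That 11.4 misstates precision for groups of 8. Its zero-event sentence is expressly about 16 vaccinees, so figures for 8 would be an addition, not a correction.

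Figure 5 in Protocol 11.4 plots exact intervals for 16 per group. Its image was not available for this check, so it may already show the correct limit.

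**Conclusion.** The concern holds, at modest weight. The zero-event statement is wrong by 0.6 percentage points under the interval that the protocol names and the SAP specifies. The pooled statement is correct for 44 or more vaccinees and too high below that, by at least 2.4 points at the permitted minimum (96.6% against more than 99%).

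These results assume independent subjects, a true rate of exactly 10% for the detection chances, and groups that split exactly 1:1. The protocol describes group sizes as approximate, so the actual totals may differ slightly.

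Nothing in the conduct of the trial depends on either figure. The holding rules use event counts and a 25% threshold with at least two infants, the early-escalation criteria in 11.4 use platelet data, and the analyses are descriptive. The points therefore do not show that the trial is too small or that any analysis is invalid. They concern only whether the stated precision is the precision the design has.

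**What to change.** Amend two sentences in Protocol 11.4:

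1. State that, with no AE among 16 vaccinees, the exact two-sided 95% CI excludes AE rates above 20.6%.
2. State that, pooled over dose levels, the chance of seeing at least one subject with an AE whose true rate is 10% runs from 96.6% with 32 vaccinees to 99.4% with 48.

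Optionally, add that a step closing with about 8 vaccinees has a zero-event upper limit of 36.9% and a 57.0% chance of showing an AE with a 10% rate. Early escalation would rest on groups of that size.

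The cost is editorial: the stated figures become slightly less favourable, and no sample size, decision rule or planned analysis changes.

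### The Bayesian platelet calculation in Protocol 11.4 has one mean for vaccine and placebo infants together and no stated likelihood SD, so its predictive probability is a poor measure of vaccine-related risk

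*Protocol*

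**What the plan says.** Protocol 11.4 describes cohorts of 32, "randomized 1:1 to vaccine or placebo". The early look comes at "16 infants per dose cohort (8 per group").

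The Bayesian part works by "treating the mean of platelet counts μ as a random variable with a normal prior distribution"; "μ_0 would be 300,000, a mean of the range, and σ_0 would be 75000". On timing and data it says: "After 16 infants complete the two-dose vaccination schedule, a posterior distribution of μ will be calculated", using the prior and the Day 31 counts. The prediction is for the next 16 subjects of the cohort, "among the future 16 subjects by basing it on what we have observed in the first 16 subjects". Section 1.2.4.1 describes the same target. A sensitivity analysis on the prior is promised, but no sampling SD is given for this model.

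Neither section includes an arm term or restricts the data to vaccinees. Elsewhere in 11.4 vaccinees are named when they are meant: in the zero-event confidence limit for 16 vaccinated subjects, in the Day 31 comparison of vaccinees with placebo recipients, and in the clause on a Grade 3 event in a vaccinated infant. The SAP does not describe the calculation.

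The IDMC may recommend moving on early if two things hold: a by-arm 95% CI criterion for the Day 31 mean difference, and a sufficiently high predictive probability, with 80% as the example.

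**The concern.** The calculation is offered as assurance against vaccine-induced thrombocytopenia. If half the counts behind the posterior, and half the infants in the prediction, received placebo, one normal mean is being fitted to a two-arm mixture. A real drop in vaccinees then reaches the result at half strength. The IDMC could be shown a reassuring probability while the vaccine arm has moved substantially. The missing SD matters as well, because the probability of a count below 50,000 is a tail area and depends heavily on it.

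**Working it through.** **The plan's own figures.** There is no numerical Bayesian result to reproduce, so the companion figures were checked first (counts in thousands/mm³).
- Background Grade 3 rate: Φ((50 − 300)/75) = Φ(−3.33) = 0.043%, matching the stated 0.04%.
- Power with 8 per group, margin 110, SD 75, one-sided 0.025, normal approximation: Φ(110/(75·√(2/8)) − 1.96) = Φ(2.933 − 1.960) = 83.5%, close to the stated 84%. The SD of 75 and the split of 8 and 8 are therefore the plan's own working values.

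**Inputs for the Bayesian part.** From 11.4: prior N(300, 75²), threshold 50, 8 + 8 infants. Assumed: a fixed sampling SD s = 75 (47.5, the other SD in 11.4, as the alternative), an observed placebo mean of 300, and an observed vaccinee mean of 300 − δ.

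**Formulas.** Posterior variance v = 1/(1/75² + n/s²). Posterior mean m = v·(300/75² + n·ȳ/s²). The predictive probability of no count below 50 among k infants is the average of [1 − Φ((50 − μ)/s)]^k over μ ~ N(m, v).

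**Dilution.** Pooled, ȳ = 300 − δ/2. With s = 75 the data weight is 16/17 pooled and 8/9 for vaccinees alone, so the posterior mean falls by 0.47δ or 0.89δ. At δ = 110:
- pooled: (300 + 16·245)/17 = 248.2
- vaccinees: (300 + 8·190)/9 = 202.2

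**Predictive probability, fixed SD 75.**

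| Observed drop δ | One pooled mean, 16 future infants | Vaccinees only, 8 future vaccinees | Vaccinees only, 16 future vaccinees | Separate arm means, 8 + 8 |
|---|---|---|---|---|
| 0 | 99% | 99% | 99% | 99% |
| 50 | 97% | 96% | 93% | 96% |
| 75 | 96% | 92% | 86% | 92% |
| 110 | 92% | 81% | 68% | 81% |
| 150 | 86% | 59% | 39% | 59% |

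The rest of a 32-infant cohort holds about 8 vaccinees, so the 8-vaccinee column is the fair comparison with the pooled one. The pooled value stays at or above 80% up to a drop of about 173; with separate arm means (8 + 8) the limit is about 112.

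**Fixed SD 47.5.** At δ = 110, pooled is just under 100% and 8 vaccinees 98%. At δ = 150 they are also just under 100% and 88%, and both meet 80%.

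**SD estimated from the pooled 16.** The between-arm difference inflates it to √(s² + δ²/4). With s = 75 this is 93.0 at δ = 110 and 106.1 at δ = 150. The pooled probability becomes about 75% and 50%, below the 8-vaccinee values of 81% and 59%.

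**The companion criterion.** With 8 per arm and SD 75, the t-based half-width is 2.145·75·√(2/8) = 80.4. If the limit is read as −110, the observed drop must be below 110 − 80.4 = 29.6. At that drop the pooled value is 98%, 8 vaccinees 98%, 8 + 8 98% and 16 vaccinees 96%.

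**The case against.** Several points can be made against this, and most of them stand in part.

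- **Inclusion of placebo is inferred.** 11.4 never says outright that placebo counts enter the posterior. The reference to 16 infants could mark when to calculate rather than whose counts to use. That is possible, but with a single μ, 16 infants defined as 8 per group and a future 16 as target, pooling is the natural reading, and nothing in the SAP corrects it.
- **Pooling does not always inflate.** A reader might infer that it does. The documents do not support that: with the SD estimated from the pooled sample the order reverses. This limits the claim but reinforces the need to state the SD.
- **A drop of 110,000 meets 80% either way.** A reader might infer that pooling alone lets the criterion be met at the frequentist margin. It does not: with SD 75,000, the vaccinee-only value for 8 future infants is 81%. The 68% is for 16 future vaccinees, a different target.
- **Other safeguards exist.** The CI is by arm and undiluted, the 80% is only an example, the IDMC recommendation is discretionary, and a Grade 3 event in a vaccinated infant is considered separately. The IDMC reviews unblinded safety data monthly (9.10.3), and holding rule 2c looks at vaccine groups only. All this stands. It means a wrong escalation decision cannot be inferred from this point. It does not make the pooled number informative, and it was added to give complementary assurance.

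**Conclusion.** The point holds as a defect in how the predictive probability is specified. As written, the sample mean carries half of any vaccine-induced drop, and the result turns on an SD the protocol does not give. With a fixed SD of 75,000, the stated prior and a placebo mean of 300,000, assurance is overstated by about 11 percentage points at a drop of 110,000 (92% − 81%) and 27 at 150,000 (86% − 59%). Only the second changes which side of 80% the figure falls. The effect is negligible for small drops.

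The stronger reading, that pooling would lead to unsafe escalation, is not supported. If the CI limit is read as −110,000, that criterion binds first (SD 75,000): it already fails above an observed drop of about 30,000, where every version of the probability is 96% or more. The printed limit has no minus sign. That is a separate inconsistency which must be reconciled, and until it is, the protection from the CI depends on how it is read.

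**What to change.** In 11.4, and in the program for the IDMC report:

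1. Fit the posterior to the Day 31 counts of vaccine recipients, or use arm-specific means.
2. Predict for the future vaccine recipients of that cohort, and say how many there are.
3. State the likelihood SD, for example estimated within arm, with 75,000 and 47,500 as sensitivity values beside the sensitivity analysis already planned on the prior.
4. Show the same quantity for placebo as reference.

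If vaccinees only was always intended, a short clarification of items 1 and 2 plus the SD is enough. No new data are needed, since the IDMC already works unblinded. The cost is wording and code. The figure will rest on 8 rather than 16 infants, so it will be less precise and usually less favourable.

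### Section 11.4 prints the 110,000 platelet bound for early escalation without a sign or order of subtraction, and its 84% power does not fit the no-effect scenario it is stated for (about 75% to 78%)

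*Protocol*

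**What the plan says.** In Protocol Section 11.4 the frequentist calculation assumes that counts in "healthy infants between 12 and 23 months follow a normal distribution with a mean of 300,000" per mm³ and an SD of 75,000. It sets against this an adverse alternative, a mean of 190,000 "with a standard deviation of 47,500". The gap of 110,000 is the decrease to be excluded, and the number needed to exclude it "with 84% power when vaccination has no effect on platelet count is 16 infants per dose cohort (8 per group". On the method: "Sample size is based on a one-sided 0.025 test of non-inferiority using the Mann-Whitney statistic", citing a PASS 12 module for two means. The PASS settings are not printed, and no sentence says which SD the vaccinated group was given.

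The last paragraph of Section 11.4 turns this into a decision aid. After the first 16 infants of a cohort have had both doses, "the 95% CI for the difference in mean platelets at Day 31 between vaccinees and placebo recipients will be calculated". "If the lower boundary of the 95% CI is above 110,000" platelets/mm³, and if the predictive probability of no Grade 3 or higher thrombocytopenia is also high enough, "the IDMC may recommend enrolling infants into the next dose cohort without completing enrolment in the current cohort".

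Section 1.2.4.1 names this calculation as one of two statistical supports for escalating on a minimum of 16 subjects.

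**The concern.** The two paragraphs should describe one procedure, and they do not match in two respects.

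- **Direction.** The sizing paragraph is about excluding a fall of 110,000. The decision paragraph asks for a lower confidence limit above a positive 110,000 and does not say which group is subtracted from which. As vaccinee minus placebo, this demands evidence that the vaccine raises the count by more than 110,000. As placebo minus vaccinee, it demands evidence of a fall larger than the one to be excluded. Neither order makes the printed bound agree with the hypothesis.
- **Power.** The 84% is given for a vaccine without effect. Vaccinated infants would then share the unvaccinated distribution, SD 75,000 included, and at 8 per group the named test falls short of 84%. The sizing also rests on a rank test, while the decision uses an interval for a difference in means.

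At stake is whether the printed criterion can be applied as written, and whether those relying on the calculation have a correct figure for how often a harmless vaccine would meet it.

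**Working it through.** **Inputs (all Section 11.4):** normal counts; SD 75,000; true difference 0; margin 110,000; one-sided 0.025, equivalent to a two-sided 95% CI; 8 per group. No dropout is stated and none is applied.

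**The plan's distributional figures reproduce.** Φ((50 − 300)/75) = Φ(−3.33) = 0.00043, the printed 0.04%. At the adverse alternative, Φ((50 − 190)/47.5) = Φ(−2.95) = 0.0016, or 0.16%.

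**Power with SD 75,000 in both groups.** The standard error of the difference is 75,000 × √(2/8) = 37,500, and 110,000/37,500 = 2.933.

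| Method | Calculation | Power |
|---|---|---|
| Known-SD normal formula | Φ(2.933 − 1.960) = Φ(0.973) | 83.5% |
| t-based CI, pooled | noncentral t, 14 df, noncentrality 2.933, critical value 2.145 | 77.9% |
| t-based CI, Welch | 500,000 simulations | 77.1% |
| Mann-Whitney, efficiency approximation | effective n = 8 × 3/π = 7.64 | 75.6% |
| Mann-Whitney, exact | critical U = 51 of 64, actual size 0.0249; two runs of 400,000 simulations | 75.3% and 75.5% |
| Efficiency factor for logistic data | effective n = 8 × π²/9 = 8.77 | about 82% |

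The logistic factor contradicts the stated normal distribution.

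**Power with SD 75,000 in one group and 47,500 in the other, true difference still 0.** The variance sum is 75² + 47.5² = 7,881 (in thousands squared).

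- Effective n of 7.64 cut to 7: standard error √(7,881/7) = 33.55 thousand, noncentrality 110/33.55 = 3.28, Welch df 10.1, power 84.05%.
- Effective n of 7.64 kept: 87.7%. Simulating the exact test with these SDs gives 87.6%, or 84.7% with a continuity-corrected normal approximation.
- t-based CI at n = 8: 89% to 90%.

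**The printed bound.** With SD 75,000 in both groups the expected half-width of the CI is about 2.145 × 37,500 = 80,400. Under no effect:

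- P(lower limit of vaccinee minus placebo > +110,000) = 1.2 × 10⁻⁶. By symmetry the reverse subtraction gives the same value.
- P(lower limit > −110,000), the event that corresponds to excluding a 110,000 fall, = 77.9%.

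**Error rate at a true 110,000 fall.** The bound implied by the hypothesis is met 2.5% to 2.6% of the time with vaccinee SD 47,500 (Welch, pooled) and 2.4% to 2.5% with SD 75,000.

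**Scale of the power gap.** Under no effect the implied bound is missed about 22% of the time with the t-based CI (100 − 77.9), and a Mann-Whitney criterion about 25% (100 − 75.3), rather than 16%. The t-based CI reaches 83.2% at 9 per group; Mann-Whitney reaches 83.7% at 10.

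**The case against.** The strongest reply on power is that Section 11.4 prints two SDs and that a combination of them yields 84.05%. A reader might infer from the 75% that the plan's figure is an arithmetic error on its own inputs, or that only a known-SD formula comes near it. The documents do not support that: the PASS settings are not shown and more than one route lands near 84%. What does not stand is that such a route justifies the sentence as written. The SD of 47,500 belongs to the 190,000 mean, so using it for vaccinees while assuming no effect mixes two scenarios. The match also needs the effective sample size cut from 7.64 to 7.

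On the sign, the intended direction can be recovered, because Sections 1.2.4.1 and 11.4 both speak of ruling out a decrease, and an IDMC would probably read it that way. That reduces the practical risk but does not repair a printed decision threshold. A minus sign lost in document conversion seems unlikely, since minus signs survive in Section 7.2, and the order of subtraction is missing in any case.

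Two further inferences should not be drawn. SAP Section 11.2 lists no method for a difference in means, but that does not show the method is undefined: under Protocol Section 11.12.1 the IDMC analyses are done by an external unblinded statistician and documented in their own report. Nor is the four-fold statement in error: the plan prints the SD of 47,500 on which it rests, and 0.16% is four times the printed 0.04%.

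Finally, Section 11.4 says that no hypothesis-driven calculation set the overall sample size. That is true of the 32 per step; the 84% is offered specifically for the reduced 16.

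**Conclusion.** Both parts hold, within limits. The escalation bound as printed conflicts with the hypothesis it was sized for: taken literally it would almost never be met by a harmless vaccine (about 1.2 in a million, against about 78% for the bound the hypothesis implies). The 84% does not fit the no-effect scenario attached to it, for which the power is about 75% for Mann-Whitney and about 78% for a t-based CI, some 6 to 9 points lower.

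A reader might infer that the overstated power makes early escalation less safe. It does not: lower power means the criterion is met less often when the vaccine has no effect, and the chance of meeting the implied bound at a true 110,000 fall stays near 2.5%. Escalation also remains a discretionary recommendation, made alongside the predictive probability and review of all safety data.

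The figures assume normal counts, SD 75,000 in both groups, independent groups and eight Day 31 counts per group. Which route produced 84% cannot be established from the documents.

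**What to change.** 1. Reconcile the sizing paragraph and the decision paragraph of Section 11.4, so that the 110,000 bound carries a sign and a stated order of subtraction consistent with the hypothesis it was sized for. Because this is a dose-escalation criterion, its final wording is for the sponsor and the IDMC to settle.
2. In Section 11.4, restate the power for the no-effect scenario as about 75% (Mann-Whitney) or about 78% (t-based CI), choosing the one that matches the method used for the CI in the decision paragraph. If 84% is kept, state the SDs and the approximation behind it and remove the no-effect wording.

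The cost is one sign and direction, one figure and one named method. Enrolment, visits and data collection are unchanged.
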